## **STATEMENT OF COMPLIANCE**

The study will be conducted in accordance with the International Conference on Harmonisation guidelines for Good Clinical Practice (ICH E6), the Code of Federal Regulations on the Protection of Human Subjects (45 CFR Part 46), and the NIDCR Clinical Terms of Award. All personnel involved in the conduct of this study have completed human subjects protection training.

## LIST OF ABBREVIATIONS

AE	Adverse Event/Adverse Experience
ATS/ERS	American Thoracic Society/European Respiratory Society
BAU	Branchial Artery Ultrasound
BP	Blood Pressure
CEMALB	Center for Environmental Medicine, Asthma and Lung Biology
CFR	Code of Federal Regulations
CRF	Case Report Form
ECG	Electrocardiogram
ELF	Epithelial Lining Fluid Collection
EPA	Environmental Protection Agency
FEV1	Forced Vital Capacity in 1 second
FA	Filtered Air
FMD	Flow Mediated Dilation
FWA	Federalwide Assurance
GCP	Good Clinical Practice
HRV	Heart Rate Variability
HIPAA	Health Insurance Portability and Accountability Act
IB	Investigator's Brochure
ICF	Informed Consent Form
ICH	International Conference on Harmonisation
ICMJE	International Committee of Medical Journal Editors
IRB	Institutional Review Board
LV	Left Ventricular
MedDRA ®	Medical Dictionary for Regulatory Activities
N	Number (typically refers to subjects)
NL	Nasal Lavage
NEC	Nasal Epithelial Cell Biopsy
NSAID	Non-Steroidal Anti-inflammatory Medications
O3	Ozone
OHRP	Office for Human Research Protections
PHI	Protected Health Information
PI	Principal Investigator
QA	Quality Assurance

[figure not shown]
QC	Quality Control
SAE	Serious Adverse Event/Serious Adverse Experience
SOP	Standard Operating Procedure
UP	Unanticipated Problem

---

## PROTOCOL SUMMARY

Title:	Human biological responses to low level ozone
Précis:	Subjects will be exposed to low levels of ozone approximating a typical, metropolitan, summer day, ranging from 0.06ppm to 0.08ppm. Subjects will be sedentary, to approximate a typical day. Nasal, pulmonary and cardiovascular endpoints will be measured.
Objectives:	Primary: To explore whether low level ozone exposure, reflective of a typical metropolitan summer day, will cause measurable inflammation in nasal cells or affect cardiovascular endpoints in a sedentary human.
Population:	15 healthy control subjects
Description of Intervention:	Subjects will be exposed to low level ozone, ranging from 0.06ppm to 0.08ppm during the course of the exposure session. Subjects will be sedentary. Nasal, pulmonary and cardiovascular endpoints will be measured.
Study Duration:	60 months.
Subject Participation Duration:	No more than 7 weeks.
Estimated Time to Complete Enrollment:	24 months.

### Schematic of Study Design

Visit 3  
Within 2 weeks  
of visit 2

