**Crossover:**  
**Repeat visit 2 as visit 5, visit 3  
as visit 6 and visit 4 as visit 7**

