#### **3.2 Subject Exclusion Criteria**

An individual who meets any of the following criteria will be excluded from participation in this study:

- Medical condition, laboratory finding, or physical exam finding including any chronic medical condition considered by the PI as a contraindication to the exposure study, including significant cardiovascular disease, diabetes requiring medication, chronic renal disease, chronic thyroid disease, or kidney disease, which precludes participation.
- Use of disallowed concomitant medications including systemic or inhaled steroids, NSAIDS or aspirin within 72 hours of dosing, and inability to withhold these medications prior to each session of the study.
- Pregnancy or nursing.

- History of current tobacco use, or more than a lifetime 5 pack year history of tobacco use.

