10. Perform nasal epithelial cell biopsy for baseline: a non-invasive biopsy procedure will be performed to retrieve a small cluster of cells from each of the nasal cavities. For the biopsy procedure, the subject will be seated comfortably in a straight-backed chair or reclining on an exam table with the head tilted as far back as possible while remaining comfortable. A short, sterile plastic sampling device called a curette will be inserted into one of the nasal cavities and the surface of the nasal cavity will be stroked several times for approximately 5 seconds in order to obtain a small cluster of cells. Only one side will be collected at this visit. The investigator, study physicians or other trained staff will collect these samples.
11. Introduce the subject to the chamber area by walking them through.
12. Subjects will be discharged with contact information for a study physician on call.

13. **Psychological surveys:** Once subjects have been qualified, they will be emailed a link to complete psychological surveys. These will be performed at home, and at the convenience of the subject, prior to the first exposure session.

Once the subject is deemed eligible, they will return for a baseline day to collect pre-exposure measurements. This visit must occur no less than 3 days and no more than 6 weeks after the screening visit. Subjects will be asked to withhold NSAIDs and antioxidant vitamins for 7 days prior, and to arrive fasting (water is acceptable). We will update any changes in medical history, including medication use, collect vital signs, and perform spirometry.

The following samples will be collected:

1. **Urine pregnancy test:** For all women, if more than 7 days have passed since the prior test.
2. **Epithelial lining fluid (ELF) collection.** This is done by having the subject spray normal saline into the nose, and then insert a small filter paper into each nostril. Nose clips are applied for 2 minutes, then the filter paper is removed. These samples are collected by study staff.
3. **Nasal lavage (NL):** This is done by repetitive spraying of sterile normal saline irrigation solution into the nostril, followed by voluntary expelling of the fluid by the subject into a specimen collection cup. Both nostrils are sampled, these samples will be collected by study staff,

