4. **Spirometry:** Standard spirometry to obtain FEV1 and FVC measurements will be done prior to sputum induction. This is done by having the subject exhale forcefully and completely into a mouth piece attached to a pneumotach. This will be repeated several times, and the procedure will be done following ATS/ERS standards.
5. **Flow-mediated brachial artery dilation (FMD):** This measurement is made by imaging the brachial artery with an ultrasound device. The blood flow to the artery is occluded for 5 minutes, and the artery is again imaged when blood flow is resumed.
6. **Left ventricular strain:** Left ventricular contractility will be assessed by measuring global longitudinal strain using 2-dimensional speckle tracking echocardiography. Apical 4-chamber, 2-chamber, and long axis 2-dimensional ultrasound images of the heart will be acquired using a Philips EPIQ 7 ultrasound machine and stored for subsequent off-line analysis. Global longitudinal strain will be quantified using Philips QLAB advanced quantification software.

The subject will be discharged to home with contact information for a study physician who is on-call if the subject has any health concerns. The subject will return the next morning, and after health history is updated and vital signs collected, the following will take place:

1. **Heart rate variability (HRV):** Standard ECG leads will be placed on the subject's chest, and connected to a monitor that records the heart rate and rhythm. The subject will be asked to lie supine in a quiet, darkened room for up to 30 minutes. The subject will do this before the exposure and immediately after the exposure. The analysis for this measurement is computer based.
2. **Spirometry:** Standard spirometry will be measured prior to the subject entering the exposure chamber.
3. **Ozone monitor:** Subjects will wear an experimental ozone monitor, which is on a bracelet. This is to validate the wearable monitor in an environment with known ozone concentration.
4. **Telemetry:** Standard 3 lead ECG monitoring will be done while the subject is in the exposure chamber.
5. **Symptom questionnaire:** Subjects will be asked to complete a symptom questionnaire prior to entering the chamber.
  

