4. ELF
5. NL
6. Spirometry
7. Sputum induction

The subjects will be discharged with contact information for a study physician. They will be scheduled to return for a second session, with a minimum of 2 weeks and a

maximum of 6 weeks between exposures. The sessions will be identical except for the atmosphere in the chamber, which is randomized.

Baseline measurements provide safety information prior to each exposure. Given the level of the O3 and the procedures that subjects are asked to undergo, we do not anticipate any health concerns, but if they do arise, they will be immediate, therefore there are no scheduled visits beyond day 3 of the 2nd session. However, subjects will be encouraged to contact the study coordinator or physician at any time up to a month later if they have any concerns regarding their health or effects from the study.

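### The schematic lets the exposure fall up to 2 weeks after the baseline visit, where Section 4 requires the next morning, and it shows one unanchored interval between sessions where Section 4 gives a range

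*Combined protocol and SAP*

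**What the plan says.** The Schematic of Study Design puts visit 3, the exposure, "Within 2 weeks" of visit 2. Its crossover box contains "Repeat visit 2 as visit 5, visit 3" as visit 6, and visit 4 as visit 7. It places visits 5 to 7 six weeks after an event that it does not name.

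Section 4 (Study Schedule) describes a baseline day and then states: "The subject will return the next morning". The exposure takes place on that return, and the follow-up visit comes 24 hours later. Section 4 closes by saying that "there are no scheduled visits beyond day 3 of the 2nd session", which fits a session of three consecutive days. It sets the interval between sessions as at least 2 weeks, with a "maximum of 6 weeks between exposures".

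Section 4 times these checks to the baseline day:

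- A urine pregnancy test: "For all women, if more than 7 days have passed since the prior test".
- A medication hold: "Subjects will be asked to withhold NSAIDs and antioxidant vitamins for 7 days prior".
- A nasal lavage, listed among the samples for that day.

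Section 3.2 adds a rule tied to the exposure itself, covering steroids and "NSAIDS or aspirin within 72 hours of dosing". It does not name vitamins.

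**The concern.** Staff often book visits from the schematic. Someone doing so here could comply with the schematic and still depart from Section 4. The checks on the baseline day are designed for an exposure about 24 hours later. If the gap grows to two weeks, they no longer describe the subject's state at exposure.

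Three things are at stake. Pregnancy is an exclusion, and the test could be stale. A subject told to hold antioxidant vitamins for the 7 days before baseline could resume them before an ozone exposure. The pre-exposure nasal lavage could be up to two weeks old, and if it serves as the reference for the change in nasal PMN counts, it is a weaker reference than one from the day before.

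The interval between sessions has a similar fault. The schematic gives a single figure with no anchor, where Section 4 gives a range counted between exposures.

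**Working it through.** **The plan's own figure.** Visit windows do not enter the sample-size calculation in Section 7, and that calculation is sound. At correlation 0, the SD of the difference is √(31² + 17²) = √1250 = 35.36. For an effect of 36, an exact two-sided paired t test at 0.05 has 92.0% power with N = 13, the smallest N that reaches 90%. This agrees with the plan. The other five cells of the table (10, 8, 10, 7, 9) also reproduce.

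**Which visit is visit 2.** The boxes for visits 1 and 2 are not visible in the text. Section 4 describes screening, baseline, exposure and 24-hour follow-up, in that order. The schematic labels the exposure visit 3 and the follow-up visit 4, and it repeats visit 2 as visit 5. A repeated visit just before the exposure is the baseline day, not screening.

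**Inputs.**

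- Baseline to exposure: 1 day (Section 4), or up to 2 × 7 = 14 days (schematic).
- Pregnancy retest at baseline: only if the prior test is more than 7 days old (Section 4).
- Screening to baseline: 3 days to 6 weeks (Section 4), so day 7 is allowed. All women are tested at screening.
- Between exposures: 2 × 7 = 14 to 6 × 7 = 42 days (Section 4).

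**Oldest pregnancy test at exposure.**

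1. First exposure: test at screening on day 0, baseline on day 7, no retest because the test is not more than 7 days old. The exposure falls on day 7 + 1 = 8 under Section 4, or day 7 + 14 = 21 under the schematic.
2. Second exposure: with exposures at least 14 days apart and each the morning after its baseline, visit 5 is at least 14 days after visit 2, so the retest always applies. It also applies under the schematic's six weeks. The test is then 1 day old under Section 4, or up to 14 days old under the schematic.

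| | Section 4 | Schematic, worst case |
|---|---|---|
| Baseline to exposure | 1 day | 14 days |
| Test to first exposure | 8 days | 21 days |
| Test to second exposure | 1 day | 14 days |

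**Vitamin hold.** It covers the 7 days before baseline. No rule ties antioxidant vitamins to the exposure, so any days between baseline and exposure are uncovered.

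**Nasal lavage.** It is listed at baseline, after the chamber, and at 24 hours. Neither the schematic's exposure box nor the visible items of the exposure-day list include one before the chamber. Item 6 of that list is not visible, so this rests on what can be read.

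**Interval between sessions.** The number of days between exposures depends on where the six weeks start:

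- Visit 3 to visit 6: 42 days.
- Visit 2 to visit 5, equal gaps in both sessions: 42 days.
- Visit 2 to visit 5, gaps differing between 1 and 14 days: 42 + 1 − 14 = 29 to 42 + 14 − 1 = 55 days.
- Visit 4 to visit 5, with next-morning exposure: 1 + 42 + 1 = 44 days.

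**The case against.** The strongest reply is that Section 4 is the operative procedure and the schematic only a summary. A site that follows Section 4 meets both texts, because the next morning lies within two weeks. That stands, and it is why this is a mismatch of windows and not a contradiction.

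A second reply is that the 21-day and 14-day figures mix sources: the interval comes from the schematic and the retest rule from Section 4. This is also fair. They are worst cases for staff who book from the schematic and test by Section 4, and they do not describe what Section 4 permits.

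Third, medication use is partly covered. Section 3.2 covers NSAIDs and aspirin in the 72 hours before dosing. Section 3.8 queries adherence to the restrictions, and Section 3.9 queries medications at each visit with physician review of new ones. What remains is antioxidant vitamins, and only if the exposure is delayed and the subject resumes them.

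Two stronger readings are tempting, and the documents do not support them:

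- **A breach of the 42-day maximum.** A reader might infer this from the 44-day figure. It requires counting from visit 4 to visit 5, and the schematic names no anchor. Other anchors give 42 days, or with unequal gaps anything from 29 to 55. The supportable statement is that a single unanchored figure stands where Section 4 gives a range.
- **Damage to the primary analysis.** A reader might infer this because Section 7 compares changes in response. But Section 2.1.1 defines the endpoint as a change between filtered air and ozone, and Section 4 says the baseline measurements provide safety information. Whether the baseline lavage enters the endpoint is therefore an inference. The documents give nothing from which to size the effect of an older baseline.

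**Conclusion.** The point holds as a minor internal inconsistency in visit timing. The schematic permits a gap of up to 14 days where Section 4 plans 1, so pre-exposure checks could be up to 13 days older than intended (21 − 8 = 13 and 14 − 1 = 13 for the pregnancy test). The interval between sessions is shown as one figure where 2 to 6 weeks is allowed.

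This rests on three assumptions: that visit 2 is the baseline day, that the parts of the schematic and exposure-day list not visible in the text add no further test, hold or lavage, and that some scheduling would be done from the schematic. No power loss is claimed. Nor is any conflict claimed with the participation limit in the Protocol Summary: the starting point of those seven weeks is not stated, and screening alone may precede baseline by up to 6 weeks.

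**What to change.** Change three labels in the schematic:

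1. *Visit 3: the morning after visit 2.*
2. *Visit 6: the morning after visit 5.*
3. *Exposures (visits 3 and 6) 2 to 6 weeks apart*, in place of the six-week label.

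With these labels, visit 5 falls 14 − 2 = 12 to 42 − 2 = 40 days after visit 4, and the worst-case test ages return to 8 days and 1 day.

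The cost is an edit to one figure. Booking from the schematic becomes less flexible, but each session already needs three consecutive days under Section 4. No visit, test or sample is added. A further rule requiring a repeat lavage when an exposure is postponed is not recommended, because it would add a visit that the plan does not foresee.

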**Exposure visit:**  
Vital signs will be collected, and subject will be queried for AEs. HRV will be obtained, spirometry performed, O3 monitor placed, telemetry placed, and symptom questionnaire obtained. A 6.5 hour exposure at O3 levels varying from 0.06 to 0.08 with the subject resting or with mild treadmill walking will take place. At the end of exposure the following samples will be collected: Symptom questionnaire, HRV, FMD, LV ultrasound, ELF and NL, spirometry.

Visit 4  
24 hours later

**Follow up visit:**  
Subjects will return 24 hours later. Vital signs and AE's will be collected. Then symptom questionnaire, HRV, venipuncture, ELF, NL, Spirometry and sputum induction will be collected.

Visit 5, 6 and 7  
6 weeks later  
Repeat intervals

**Crossover:**  
**Repeat visit 2 as visit 5, visit 3  
as visit 6 and visit 4 as visit 7**

## **1 INTRODUCTION: BACKGROUND INFORMATION AND SCIENTIFIC RATIONALE**

### **1.1 Background Information**

Air pollutants including ozone have been implicated in affecting health outcomes. In particular, high level ozone exposure has been shown to affect pulmonary function and cause pulmonary inflammation (Silverman, 1976; Hazucha 1987; Devlin, 1991). Troubling community-based work has implicated high ozone levels as being correlated with increased pediatric asthma ED visits (Strickland, 2010). Because of adverse health effects, EPA standards for safe ozone levels have been set, currently at 0.07 ppm (2008). Still, it is estimated that 100 million Americans live in areas where ozone levels periodically remain above the EPA standard. And while this EPA standard had been set based on available data, it remained unclear at the time whether low-level ozone exposure, such as 0.06 ppm, might affect health as well.

Our group previously examined lung function and inflammatory response in adults exposed to low-level ozone, 0.06 ppm exposure for 6.6 hours, while undergoing intermittent moderate exercise (Kim, 2011). We found that in response to low-level ozone exposure (0.06 ppm) with exercise, lung function declines and neutrophilic airway inflammation is observed. What remains unclear, is whether low-level ozone alone – without exercise – will cause similar health effects. If low-level ozone exposure causes measurable decrements in lung function in patients at rest, in a typical, sedentary day, this would be important for human health.

### **1.2 Rationale**

The purpose of this study is to assess the response in healthy adults to low-level ozone exposure (0.06-0.08 ppm) during a 6.6 hour sedentary day. Specifically, we will assess effect of low-level ozone exposure on the following outcomes: changes in profile of nasal inflammatory cells, lower respiratory function, and systemic cardiovascular measures such as heart rate variability, blood pressure, fibrinogen, CRP, and lipid profiles.

### **1.3 Potential Risks and Benefits**

#### ***1.3.1 Potential Risks***

##### Ozone exposure:

Exposure to ozone has been studied at our institution and by other investigators and has shown minor effects in lung function in some individuals. Subjects may experience some degree of airway irritation or cough with exposure. These symptoms typically disappear 2 to 4 hours after exposure, but may last longer for particularly sensitive people. In the unlikely event that a subject develops medically significant symptoms

during the exposure period, the exposure will be terminated and the appropriate medical intervention will be provided by the physician on site. Exposure to ozone below 0.08 ppm tends not to cause noticeable effects in most people, and 0.12 ppm is a level many people in the United States may be frequently exposed to, especially in the summer months. Our subjects' maximum exposure will be 0.08 ppm.

*Spirometry:*

Lung function testing may cause lightheadedness with repeated efforts, but this is unusual. Subjects will be seated in a non-rolling chair, and will be instructed to let us know if they feel at all lightheaded during the breathing test. We would then wait longer between each test in order to prevent lightheadedness

*Sputum collection (induction):*

Collection of sputum may cause wheezing in some individuals, and coughing repeatedly may make a subject's chest hurt. A physician is immediately available and rescue bronchodilator albuterol is on hand. Subjects will be carefully monitored with pulmonary function testing to ensure a return to baseline before leaving the research lab. Most people can do this test without any problem.

*Brachial artery ultrasound:*

There are no significant risks associated with ultrasound imaging of the brachial artery, or with the 5 minutes of reduced blood flow that is part of the test. Cutting off blood flow to the arm may result in mild discomfort or temporary sensations of tingling or numbness in the hand until the blood pressure cuff is released. About 1 in 200 patients develop a painless rash on the arm where the blood pressure cuff is placed; this disappears over several days.

*Ultrasound of the heart:* There is no risk to this procedure.

*Blood sampling from vein:*

Risks with having blood drawn include mild discomfort or bruising at the site. A small risk of infection also exists. Blood will be drawn by well-trained staff.

*Ambulatory ECG monitoring (Holter):*

Subjects may have minor skin irritation in the area where the electrodes are attached to the skin. Prior to electrode application, the skin will be treated with alcohol and a cleansing solution. If male, the skin will be shaved in the area where the electrodes are attached. Subjects should not participate if skin is highly sensitive to electrode adhesive or gel. Subjects will not be able to do activities which would result in the monitor getting wet, such as showering or swimming while the monitor is on.

*Nasal lavage and ELF procedure:* There are no risks associated with the nasal lavage. The ELF can sometime make individuals sneeze.

*Nasal epithelial cell collection:* This procedure can cause mild temporary bleeding from the nose. It will be treated if it occurs by squeezing the tip of the nose for 5-10 minutes. Nasal biopsy also is transiently painful.

*Genetic sampling:*

There is risk of discrimination based on results. A Federal law, the Genetic Information Nondiscrimination Act (GINA), generally makes it illegal for health insurance companies, group health plans, and most employers to discriminate against subjects based on genetic information. GINA does not protect subjects against genetic discrimination by companies that sell life insurance, disability insurance, or long-term care insurance. GINA does not protect subjects against discrimination based on an already-diagnosed genetic condition or disease.

*Confidentiality:* There is risk of breach of confidentiality of medical information and/or data. All individuals who have been granted access to the data to perform their research-related duties will be bound by an agreement of confidentiality. Blood and sputum samples will be stored until all measurements are made for this study. Any samples that are left over will continue to be stored. We will give subjects a consent form which discusses sample storage, titled "Center for Environmental Medicine, Asthma, and Lung Biology Repository for storage of coded samples" (05-2528). Subjects are not required to provide permission for us to store these samples after this study is completed in order to participate in this study.

*Psychological questionnaires:* It is possible that subjects might find the questions asked in the surveys to be upsetting. These questions are not meant to be intentionally upsetting, but personal questions have a small potential to cause psychological stress. Subjects are not required to answer any questions with which make you uncomfortable.

There may be uncommon or previously unknown risks. You should report any problems to the researcher.

